4.8.5 Vital Signs

Respiratory rate (breaths per minute), heart rate (beats per minute), systolic and diastolic blood pressure (mmHg) and body temperature (°C) will be summarised overall and by treatment group at each applicable visit by means of descriptive statistics. Absolute and percentage changes from baseline to each visit after the first IMP dose will also be summarised. The number and percentage of subjects with Normal, Abnormal NCS and Abnormal CS results will be presented.

A shift table will also be provided for the clinical assessment. This will show the shift from baseline to each post-baseline visit, as well as to the worst overall result assessed at any visit after baseline, including unscheduled visits.

Additionally, for the Visit 7 summary, statistics for weight (kg) and BMI (kg/m²) will be presented.

Notes:

- BMI will be computed as weight at Visit 7 (kg) / (height at Visit 1 [m²]);
- Change from baseline for each parameter will be computed using the formula:

$$\text{Change (unit)} = \text{AVAL (unit)} - \text{baseline AVAL (unit)};$$

- Due to CTP amendments and to the corresponding changes in the procedures schedule and due to differences in the schedule of assessments in the local versions of the CTP, not all the subjects have undergone the same sequence of vital sign assessments. All the values collected will be summarised jointly. Considering the presence of a stratified and permuted blocks randomisation, list no imbalance between treatments is expected.

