9.1. VISIT 1 - SCREENING VISIT (WITHIN 45 DAYS OF VISIT 2)

At Visit 1 (Screening), the following procedures will be performed:

- obtain written Informed Consent (including separate written Informed Consent for subjects participating in the pharmacokinetic sub-study at selected sites);
- documentation of medical history and subject demographic data;
- documentation of previous and concomitant medications (including long term antibiotic use for NCFB pulmonary infection prophylaxis and, in particular, azithromycin/erythromycin/clarithromycin administration in the last 12 months, and any prior use of nebulised colistin or colistimethate sodium or other inhaled/oral antibiotic);
- check number of NCFB pulmonary exacerbations in the preceding year;
- check of inclusion/exclusion criteria;
- assessment of vital signs ([Section 10.1.3](#));
- physical examination (including chest auscultation);
- 12-lead ECG in the supine position after 5 minutes of rest (evaluation by local medical staff) in order to verify the subject’s eligibility ([Section 10.1.6](#));
- blood samples for clinical laboratory assessments (haematology, clinical chemistry and renal function tests) ([Section 10.1.4](#));
- dip-stick pregnancy test for women of child-bearing potential.
- spirometry (if not done in the 30 days beforehand); pre-bronchodilator FEV₁ must be ≥25% of predicted for the patient normal value (determined using Global Lung Function Initiative [GLI] reference equations);
- collection of sputum samples for *P. aeruginosa* CCI [REDACTED] (results have to be available by Visit 2; if negative, the subject will be asked to return to the clinic for a repeat sputum sample prior to Visit 2 - if this second sample is also

negative, one further sample may be collected for analysis; thereafter, the subject will be a screen failure and will not be required to attend Visit 2);

- instruction of subjects on actions to be taken in case of NCFB pulmonary exacerbations.

The Investigator will arrange an appointment for Visit 2 within 45 days.

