10.1.4. LABORATORY EVALUATIONS

Routine laboratory evaluations will be performed at the Screening Visit (Visit 1), Visit 5, and Visit 7. The haematology and clinical chemistry parameters detailed in Table 1 will be analysed at the central laboratory using standard, validated laboratory methods.

Renal function will be monitored by laboratory tests (creatinine, Blood Urea Nitrogen [BUN]) performed at the Screening Visit (Visit 1) and during the treatment: at Day 28 of treatment (Visit 3), after 6 months (Visit 5), and at the end of treatment (Visit 7).

Subjects with clinically relevant impaired renal function (as defined by serum creatinine levels $\geq 2.0x$ upper limit of normal) will be discontinued.

Note that at Visit 1 and Visit 7 the blood samples for these assessments must be collected after the 12-lead ECG assessments have been performed.

A dipstick urine pregnancy test for women of child-bearing potential will be performed at the investigational site at the Screening Visit (Visit 1) and at all scheduled study visits thereafter.

Female subjects who become pregnant during the trial must be withdrawn from the trial without delay and will be followed up to determine the outcome of the pregnancy. The Investigator is required to inform the Sponsor of a subject's pregnancy and the estimated date of delivery. Reporting requirements are outlined in [Section 17.10](#).

Clinical laboratory tests will be reviewed for results of potential clinical significance before Visit 2 to confirm patient's eligibility and during the trial, as appropriate.

Clinically significant laboratory abnormalities arising from Visit 2 onwards are considered to be AEs. Where possible, a diagnosis should be ascribed to the abnormal lab test.

Table 1 CLINICAL LABORATORY EVALUATIONS

Haematology: at the Screening Visit (Visit 1), Visit 5, and Visit 7			
Haematocrit	Haemoglobin	Platelet count	Red blood cell count
White blood cell count and differential (neutrophils, lymphocytes, monocytes, eosinophils and basophils)			
Clinical Chemistry: at the Screening Visit (Visit 1), Visit 5, and Visit 7			
BUN*	Chloride		AST
Creatinine*	Uric acid		ALT
Sodium	Amylase		GGT
Potassium	ALP		Bilirubin (direct and total)
Calcium			
Pregnancy Test (women of child-bearing potential only):			
Urine β -hCG (dipstick) at the Screening Visit (Visit 1) and at all visits thereafter			
* These evaluations will also be performed at Visit 3			

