3.3 Study Schedule

The current trial will include 7 planned clinical visits at the investigational site, 1 telephone call 7 days after commencing treatment and 1 follow-up telephone call two weeks after discontinuation of treatment, as detailed in Section 9 of the CTP. A detailed flow chart of CTP Version 4.0 showing the procedures performed is given below in Table 3.3.1.

Additional procedures are scheduled for France sites according to CTP Version 4.0-FRA, as reported in Table 3.3.2.

CONFIDENTIAL

Sponsor:	Zambon S.p.A.	Protocol Number:	Z7224L02
----------	---------------	------------------	----------

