4.1.6 Definition of Baseline

Age, height, weight and Body Mass Index (BMI) recorded at Visit 1 will be presented as baseline characteristics.

For 12-lead ECG, vital signs, physical examination and haematology, clinical chemistry and renal function parameters, baseline values are those recorded at Screening (Visit 1). If no assessment has been conducted at that visit, the last available value before IMP first dose (collected during unscheduled visits before IMP first dose) will be considered as baseline.

For sputum analysis, **CCI** and spirometry baseline values are those recorded at Visit 2 before IMP first dose. If no assessment has been conducted at that visit, the last available value before IMP first dose (collected at the Screening visit or unscheduled visits before IMP first dose) will be considered as baseline.

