4.8.4 Haematology, Clinical Chemistry and Renal Function Parameters

The following haematology and clinical chemistry (including renal function) parameters will be summarised.

Category	Parameter	Unit
Haematology	Haemoglobin	g/L
	Haematocrit	L/L

CONFIDENTIAL

Sponsor:	Zambon S.p.A.	Protocol Number:	Z7224L02
----------	---------------	------------------	----------

	Red Cell Count	x10E12/L
	White Cell Count	x10E9/L
	Neutrophils	%
	Total Lymphocytes	%
	Monocytes	%
	Eosinophils	%
	Basophils	%
	Neutrophils (Abs)	x10E9/L
	Total Lymphs (Abs)	x10E9/L
	Monocytes (Abs)	x10E9/L
	Eosinophils (Abs)	x10E9/L
	Basophils (Abs)	x10E9/L
	Platelets	x10E9/L
Chemistry	Sodium	mmol/L
	Potassium	mmol/L
	Chloride	mmol/L
	Uric Acid	mmol/L
	Bilirubin (Total)	umol/L
	Bilirubin (Conj)	umol/L
	AST	U/L
	ALT	U/L
	GGT	U/L
	ALP (Alk Phos)	U/L
	Calcium	mmol/L
	Amylase	U/L
Renal Function	BUN (Urea)	mmol/L
	Creatinine	umol/L

Results as assessed at each applicable visit will be summarised by treatment group and overall using descriptive statistics for continuous variables. Absolute and percentage changes from baseline will also be presented.

A shift table will also be provided presenting results as lower than, within and higher than the central laboratory normal range. This will show the shift from baseline to each post-baseline visit, as well as to the most extreme value (defined as the value furthest outside [below or above] the central laboratory normal range) at any visit after baseline, including unscheduled visits.

Notes:

- Change from baseline for each parameter will be computed using the formula:

$$\text{Change (unit)} = (\text{AVAL [unit]} - \text{baseline AVAL [unit]});$$

- All results outside the central laboratory normal range will be flagged in the data listings;

CONFIDENTIAL

Sponsor:	Zambon S.p.A.	Protocol Number:	Z7224L02
----------	---------------	------------------	----------

- Repeat laboratory results within a visit will replace the original value;
- Due to CTP amendments and to the corresponding changes in the procedures schedule and due to differences in the schedule of assessments in the local versions of the CTP, not all the subjects have undergone the same sequence of laboratory assessments. All the values collected will be summarised jointly. Considering the presence of a stratified and permuted blocks randomisation list, no imbalance between treatments is expected.

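### The worst-value safety shift tables in SAP 4.8.4 to 4.8.7 have no lower bound at first dose, so a pre-dose result can be counted as a post-baseline outcome

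*SAP*

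**What the plan says.** SAP 4.1.6 sets baseline for ECG, vital signs, physical examination and laboratory parameters: "baseline values are those recorded at Screening (Visit 1"). If nothing was recorded at Visit 1, the last value before first dose ("collected during unscheduled visits before IMP first dose) will be considered as baseline") takes its place. The SAP therefore foresees unscheduled pre-dose visits for these assessments.

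The worst-value column is defined in the same way in four places. The vital-sign shift table (4.8.5) goes to each post-baseline visit, "as well as to the worst overall result assessed at any visit after baseline, including unscheduled visits". Physical examination (4.8.6) and ECG (4.8.7) use the same words for the worst result. The laboratory table (4.8.4) takes the most extreme value "at any visit after baseline, including unscheduled visits".

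Two other rules are anchored to first dose. The vital-sign change summaries in 4.8.5 read "Absolute and percentage changes from baseline to each visit after the first IMP dose will also be summarised". In SAP 4.8.1 an adverse event is treatment-emergent only from the date of first dose, with a same-day question for events that preceded it.

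SAP 4.1.11 keeps unscheduled assessments out of the analysis unless a section states otherwise. The four shift-table sections do state otherwise.

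**The concern.** A post-baseline safety table should show what happened after drug was given. Here baseline is normally the Visit 1 value, and Visit 2, the day of first dosing, may follow up to 45 days later (Protocol 9.1; case-by-case extension under Covid-19 in Protocol 7.1). A result from that interval is after baseline but before any exposure. The literal rule places it in the worst-value column beside results obtained on drug or placebo.

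The tables are read by arm. A pre-dose abnormality cannot be caused by the study drug and, under randomisation, should be equally frequent in both arms. Counting it adds background to both percentages, which tends to hide a difference. It also leaves the window to the programmer, because the same section uses two different starting points.

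**Working it through.** The plan gives no figure for this point, so there is none to reproduce. The check has two parts: what the rules admit, and how much that could matter under stated assumptions.

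**What can fall between Visit 1 and first dose**

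- *Main protocol, scheduled:* none. Vital signs and physical examination are at Visits 1 and 7 and at exacerbation visits. Routine laboratory tests are at Visits 1, 5 and 7, with renal function also at Visit 3. ECG is at Visits 1 and 7 (Protocol 10.1.2 to 10.1.4, 10.1.6, Appendix 1).
- *Unscheduled, all four domains:* possible. Protocol 10.1.4 says "Clinical laboratory tests will be reviewed for results of potential clinical significance before Visit 2", and Protocol 10.1.6 allows ECGs to be repeated if needed. Neither says how often this happens. A laboratory repeat within Visit 1 replaces the original (SAP 4.8.4) and so becomes the baseline. A repeat at a separate unscheduled visit is not covered by that rule.
- *France:* "Additional procedures are scheduled for France sites according to CTP Version 4.0-FRA" (SAP 3.3). The French chart in SAP 3.3.2 marks vital signs at Visit 2, Day 0, without saying whether they precede the dose. Protocol 10.1.3 places vital signs before spirometry at Visits 1 and 7, and Visit 2 spirometry starts before the first dose (Protocol 9.2). If French sites keep that order, these readings are pre-dose. This is an inference, since the French protocol is not among the documents. By the same logic, French Visit 2 would qualify as a post-baseline visit row in the vital-sign shift table.

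**Direction and size (all risks are assumptions)**

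Let p be the risk of at least one post-dose abnormality in an arm. Let q be the share of subjects with a pre-dose abnormality, the same in both arms and independent of the post-dose result. Then

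observed risk = p + (1 − p)q, and observed difference = (1 − q)(p₁ − p₀).

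Example with p₀ = 0.10, p₁ = 0.20, q = 0.05:

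- placebo: 0.10 + 0.90 × 0.05 = 0.145
- drug: 0.20 + 0.80 × 0.05 = 0.240
- difference 9.5 points, ratio 0.240/0.145 = 1.66

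| Assumed risks | q | Observed | Difference (points) | Ratio |
|---|---|---|---|---|
| 10% v 20% | 0 | 10.0% v 20.0% | 10.0 | 2.00 |
| | 1% | 10.9% v 20.8% | 9.9 | 1.91 |
| | 2% | 11.8% v 21.6% | 9.8 | 1.83 |
| | 5% | 14.5% v 24.0% | 9.5 | 1.66 |
| | 10% | 19.0% v 28.0% | 9.0 | 1.47 |
| 2% v 6% | 0 | 2.0% v 6.0% | 4.0 | 3.00 |
| | 1% | 3.0% v 6.9% | 4.0 | 2.33 |
| | 5% | 6.9% v 10.7% | 3.8 | 1.55 |

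The difference barely moves at small q. The ratio for a rare abnormality is more sensitive.

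A realistic q is itself a product: the share of subjects with any pre-dose reading times the chance that it is abnormal. If 5% have a pre-dose repeat and 5% of repeats are abnormal, q = 0.05 × 0.05 = 0.0025. Risks of 5% v 10% then become 0.05 + 0.95 × 0.0025 = 5.2% and 0.10 + 0.90 × 0.0025 = 10.2%. The difference stays at 5.0 points and the ratio falls from 2.00 to 1.95.

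**The case against.** The strongest reply is that very little data can enter the gap. The main schedule has nothing there, and within-visit laboratory repeats replace the original. A clinically significant ECG abnormality at Visit 1 excludes the subject (Protocol 10.1.6), and exclusion criterion 18 removes significant screening abnormalities that endanger safe participation. All of this stands. It limits how many results are affected but does not close the window. For example, an abnormal but not clinically significant ECG at an unscheduled pre-dose visit would still qualify.

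The French case is also uncertain. The chart comes from country version 4.0, the version 5.0 flow chart has no vital signs at Visit 2, and the number of French subjects is not given. That too stands, although readings already taken under the French schedule would remain in the data.

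The tables are descriptive, with no planned test. Shifts to scheduled post-dose visits stay correct in their own rows. Clinically significant abnormalities are also reported as adverse events, whose tables are anchored to first dose. A persistent abnormality already present at Visit 1 sits in the abnormal-baseline row and is not a new shift, so the independence formula overstates the contamination.

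A reader might go further and infer that safety differences will be materially diluted. With a 5% abnormality chance per reading, doubled by drug, one post-dose reading gives 10.0% v 5.0% (ratio 2.00). One added pre-dose reading gives 1 − 0.90 × 0.95 = 14.5% v 1 − 0.95 × 0.95 = 9.8% (ratio 1.49). That holds only among subjects who all had a pre-dose reading, not for the whole table. The documents supply neither the probabilities nor the number of such subjects.

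**Conclusion.** The drafting gap is real. As written, the worst-value window in 4.8.4 to 4.8.7 admits pre-dose results, in conflict with the first-dose anchor in 4.8.5's change summaries and in the adverse event rule. Any pre-dose abnormality so counted is misclassified, however rare.

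The size cannot be computed from the documents and is probably small. The direction rests on two assumptions: pre-dose abnormalities are unrelated to arm, and drug does not lower the risk of abnormality. Then including them can, in expectation, only pull the comparison towards no difference. Chance imbalance in a single trial could go either way.

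Two stronger readings are not supported. Baseline is not rigidly fixed at Visit 1, because there is a last-pre-dose fallback. Dilution is a possibility under the rule, not an established feature of this trial's data. No hypothesis test or efficacy result is touched.

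**What to change.** In SAP 4.8.4, 4.8.5, 4.8.6 and 4.8.7, define the worst or most extreme value as taken at any assessment after the first IMP dose, including unscheduled ones. Apply the same lower bound to the post-baseline visit rows of the shift tables in 4.8.4 to 4.8.6. Show pre-dose results in listings only.

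A date filter alone cannot separate readings on the day of first dose. Add a line saying how these are classified, in particular French Visit 2 vital signs: for example, as pre-dose unless a recorded time shows otherwise. The documents do not say whether a time is recorded.

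The cost is one phrase in four sections, one same-day rule and a filter in the shift-table programs. No information is lost, because SAP 4.1.12 already lists all data. If the blind has been broken, the SAP's own rule on later deviations applies and the change should be labelled post hoc.

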4.8.6 Physical Examination Results

Physical Examination findings collected at each visit will be described by treatment group and overall presenting the number and percentage of subjects with Normal, Abnormal NCS and Abnormal CS results for each body system as per the eCRF. Results for other body systems collected, but not specified in the eCRF will be listed only.

A shift table will also be provided. This will show the shift from baseline to each post-baseline visit, as well as to the worst overall result assessed at any visit after baseline, including unscheduled visits.

CONFIDENTIAL

Sponsor:	Zambon S.p.A.	Protocol Number:	Z7224L02
----------	---------------	------------------	----------

Notes:

- Due to CTP amendments and to the corresponding changes in the procedures schedule and due to differences in the schedule of assessments in the local versions of the CTP, not all the subjects have undergone the same sequence of physical examinations. All the values collected will be summarised jointly. Considering the presence of a stratified and permuted blocks randomisation list, no unbalance between treatments is expected.

4.8.7 12-Lead ECG

The 12-lead ECG overall interpretation at Visit 1 and Visit 7 will be described by treatment group and overall presenting the number and percentage of subjects with Normal, Abnormal NCS and Abnormal CS results. A shift table will also be provided showing the change from baseline to Visit 7, as well as to the worst overall result assessed at any visit after baseline, including unscheduled visits.

4.8.8 Pregnancy Test

Results from dipstick urine pregnancy tests for women of child-bearing potential will be listed only.

4.8.9 Other Data

All other data collected in the eCRF will be listed only.

4.9 Adjustment for Covariates

The adjusted mean annual NCFB pulmonary exacerbation rate will be estimated by a negative binomial model including treatment, use of stable concomitant therapy with oral macrolides (e.g. azithromycin or erythromycin or clarithromycin: Yes/No) and country, as detailed in Section 4.9.1, as fixed effects and log-time on treatment as an offset. An exploratory model will also be fitted considering the number of CCI requiring oral/intravenous antibiotics in the last 12 months prior to study entry.

The Cox proportional hazard regression model for CCI will include use of stable concomitant therapy with oral macrolides (e.g. azithromycin or erythromycin or clarithromycin: Yes/No) and country, as covariates.

In the analysis of CCI total score and CCI domain scores, a linear mixed model for repeated measures will be applied. This will include treatment, visit, treatment-by-visit interaction, use of stable concomitant therapy with oral macrolides (e.g. azithromycin or erythromycin or clarithromycin: Yes/No) and country, as fixed effects and baseline value as covariate.

The CCI CCI will be analysed by means of a linear mixed model for repeated measures including treatment, country, and use of stable concomitant therapy with oral macrolides (azithromycin or erythromycin or clarithromycin: Yes/No) as fixed effects and baseline value as covariate.

CONFIDENTIAL

Sponsor:	Zambon S.p.A.	Protocol Number:	Z7224L02
----------	---------------	------------------	----------

4.9.1 Country Effects

Sites are too numerous to be fitted in any model based analysis, therefore sites will be clustered under country with country included in modelling as a fixed effect. Given the similarity in geographic characteristics and concomitant treatments used (other than oral macrolides: i.e. bronchodilators, corticosteroids, etc) this approach is considered reasonable.

Smaller countries, with very few subjects, will be grouped into a single ‘Other’ country category. Based upon blinded trial data, the smaller countries to be grouped together the under ‘Other’ category are: Germany (N=3), Greece (N=3), Israel (N=4), Italy (N=1), New Zealand (N=6) and Portugal (N=2)..

Any change from this strategy will be discussed at the blind review meeting and documented in the Blind Data Review and Analysis Sets Report.

4.10 Protocol Deviations

4.10.1 Major Protocol Deviation Criteria

Exact definitions of major protocol deviations affecting safety and efficacy analyses will be discussed at the blind review meeting and documented in the Blind Data Review and Analysis Sets Report. The Protocol Deviation and Non-Compliance Management Plan documents the process for identifying protocol deviations that would potentially exclude subjects from the PP Population.

If major protocol deviations occur as outlined in the criteria below, then the data from complete individual subjects, individual visits or individual evaluations will be excluded from the population of analysis as indicated.

Exclusion of subjects or observations from the analyses will be decided jointly by the CRO and Sponsor’s Study Team prior to unblinding of the randomisation code and database release.

The subjects or observations to be excluded, and the reasons for their exclusion, will be documented and approved by the above-mentioned persons prior to database release. The documentation will be filed together with the remaining trial documentation.

The number of subjects in each analysis population will be reported. Major protocol deviations excluding subjects from any particular population will be described, reporting the number of protocol violators for each criterion. All major protocol deviations will be listed and summarised for all screened subjects.

Major protocol deviations will be classified according to the following categories:

- Concomitant Medication / Administration of Prohibited Medication;
- Inclusion or Exclusion Criteria;
- Informed Consent / ICF not signed or signed late;
- Informed Consent / Other;
- Investigational Product / Incorrect IMP kit given to subject;
- Investigational Product / IMP Dosing;
- Investigational Product / IMP Storage;

CONFIDENTIAL

Sponsor:	Zambon S.p.A.	Protocol Number:	Z7224L02
----------	---------------	------------------	----------

- Investigational Product / Other;
- Met Withdrawal Criteria but was not Withdrawn;
- Patient Privacy (PP) / PP not signed;
- Patient Privacy / Other;
- Randomization / Mis-stratification;
- Randomization / Multiple Randomizations;
- Randomization / Other;
- Randomization / Randomized Not Treated;
- Randomization / Treated and Not Randomized;
- SAE not reported or reported late;
- Study Procedure / Missed procedure;
- Study Procedure / Other;
- Study Procedure / Site Staff Authorization, Delegation, Training;
- Study Procedure / Subject compliance;
- Study Procedure / Unmasking (not per protocol);
- Study Procedure / Visit Missing;
- Study Procedure / Washout;
- Visit Window.

These categories may be amended or other categories may be added, but any changes will be made prior to database lock and will be documented in the Blind Data Review and Analysis Sets Report.

